2. STATISTICAL HYPOTHESES

Not applicable.

3. SAMPLE SIZE DETERMINATION

Not applicable.

4. POPULATIONS (ANALYSIS SETS) FOR ANALYSIS

In GRIPHON (A302) and GRIPHON OL (A303), two consecutive trials, a participant could go through one or more periods, which form a specific treatment sequence from A302 to A303 as summarized in [Table 2](#). For each treatment sequence a participant is counted only once.

Table 2: Summary of Consecutive GRIPHON (A302) and GRIPHON OL (A303) Studies (Periods) and Treatment Sequence

| Treatment sequence | Consecutive periods for ADaM datasets | |
|----------------------------|---|---|
| | Period 1 | Period 2 |
| | AC-065A302 (A302) | AC-065A303 (A303) |
| Selexipag / selexipag | Selexipag ←----- analysis phase 1 -----→ ←----- analysis -----→ | Selexipag ←----- analysis phase 2 -----→ ←----- analysis phase 3 -----→ |
| Selexipag / not applicable | Selexipag ←----- analysis phase 1 -----→ ←----- analysis phase 3 -----→ | Not entered in Period 2 |
| Placebo / selexipag* | Placebo ←----- analysis phase 1 -----→ | Selexipag ←----- analysis phase 2 -----→ ←----- analysis phase 3 -----→ |

*Participants who received Placebo in A302 and did not enter in A303 are not shown because they are not included in any analysis per this SAP.

To provide comprehensive long-term safety information, two analysis sets will be used and are defined as follows ([Table 3](#)):

Table 3: Description of Analysis Sets

| Analysis Sets | Description |
|-----------------------------------|---|
| Treated Set – OL | The treated set - OL (OLS) includes all participants who received at least one dose of study intervention in the A303. This is a subset of the Selexipag-Treated Set defined below. Under this Analysis set, the following three groups will be summarized: 
 - Ex-Selexipag: participants who received Selexipag in A302 - Ex-placebo: participants who received placebo in A302 - Total A303 This analysis set consists of data collected during “Analysis phase 2” in Table 2 (baseline (BL) is defined in Section 5.1.5.1) |
| Selexipag-treated Set (A302+A303) | The Selexipag-treated set (STS) includes all participants who received selexipag treatment at any time during A302 or A303. Under this Analysis set, the following two groups will be summarized: |

Table 3: Description of Analysis Sets

| Analysis Sets | Description |
|---------------|---|

5. STATISTICAL ANALYSES

5.1. General Considerations

This is an open-label extension study. No formal hypothesis testing will be conducted. Data will be summarized using descriptive statistics. Continuous variables will be summarized using the number of observations, mean, SD, median, and range as appropriate. Categorical values will be summarized using the number of observations and percentages as appropriate. No efficacy analysis is expected.

5.1.1. Visit Windows

As participants do not always adhere to the protocol visit schedule, the following rules are applied to assign actual visits to analysis visits on A302 and A303. [Table 4](#) lists the visit windows and the target days for planned visits. The reference day is Study Day 1 (Section [5.1.2](#)). If a participant has 2 or more actual visits in 1 visit window, the visit closest to the target day will be used as the protocol visit for that visit window. The other additional visit(s) will not be used in the summaries or analyses, but they can be used for determination of clinically important endpoints. If 2 actual visits are equidistant from the target day within a visit window, the later visit is used.

All assignments will be made in chronological order. Once a visit date is assigned to a visit window, it will no longer be used for a later time point. Listed below are the analysis visit windows and the target days for each visit defined in the protocol.

Table 4: Visit Windows

| Parameter | Visit Number | Time Interval (label on output) | Time Interval (Day)* | Target Time Point (Day) |
|-------------------|--------------|---------------------------------|-----------------------|-------------------------|
| Safety parameters | 1 | Baseline | No limit – to 1 | 1 |
| | 2 | Week 4 | 2 to 42 | 28 |
| | 3 | Week 8 | 43 to 84 | 56 |
| | 4 | Week 16 | 85 to 147 | 112 |
| | 5 | Week 26 | 148 to 270 | 182 |
| | 6 | Month 12 | 271 to 450 | 360 |
| | 7 | Month 18 | 451 to 630 | 540 |
| | 8 | Month 24 | 631 to 810 | 720 |
| | 9 | Month 30 | 811 to 990 | 900 |
| | 10 | Month 36 | 991 to 1170 | 1080 |
| | 11 | Month 42 | 1171 to 1350 | 1260 |
| | 12 | Month 48 | 1351 to 1530 | 1440 |
| | 13 | Month 54 | 1531 to 1710 | 1620 |
| | 14 | Month 60 | 1711 to 1890 | 1800 |
| | x | Month n | n×30-89 to n×30+90 | n×30 |

*Relative to Study Day 1 (Section [5.1.3](#)).

**Visit x corresponds to an interval of every 6 months.

For safety analysis, only assessments measured during the treatment period (i.e., from study intervention start up to 3 days after study intervention discontinuation, limits included) are considered in the time interval of Month n (i.e., an interval of every 6 months).

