¹ For patients on study treatment until unblinding of AC-065A302/GRIPHON, Visit 1 should correspond to the last visit in the double-blind study AC-065A302/GRIPHON or, if not possible, must be within 2 weeks (14 days); ² Not applicable, patient will switch directly from Visit 1 to Week 12 phone call and Visit 5; ³ Monthly urine (or serum) pregnancy test for women of childbearing potential until 1 month after study drug discontinuation; ⁴ Scheduled telephone call. ⁵ Hematology and blood chemistry tests to be performed at Visit 1 only if the last assessment in AC-065A302/GRIPHON was performed more than 4 weeks before, and then at every visit until EOS. ⁶ Physical examination results will not be collected in the CRF but clinically relevant changes from baseline must be reported as adverse events. ⁷ Throughout the course of the study, it is recommended to regularly discuss with the patient whether new PAH therapy is becoming available.

* 6 months correspond to 26 weeks.

CRF = Case Report Form; EOS = End of Study; EOT = End of Treatment; NA = Not applicable.

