3.10.3 Maintenance period

3.10.3.1 Visit 5 and 6-monthly visits (Visit 6, 7, etc.)

From Visit 5 onwards, all following visits are scheduled every 6 months \pm 7 days. In between the 6-monthly visits, the investigator will call the patient to assess safety and tolerability by inquiring about AEs and SAEs.

The morning dose of the study drug should be taken as usual.

These visits include:

- Physical examination
- Recording of AEs/SAEs
- Concomitant medication
- Measurement of vital signs and body weight
- Laboratory tests including:
 - Hematology
 - Blood chemistry
- Urine pregnancy test (for women of childbearing potential)
- Dispensing of study drug (selexipag) for a 6 months' treatment period.

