3.10.6 Unscheduled visits

Unscheduled visits may be performed at any time during the study. Depending on the reason for the unscheduled visit (e.g., loss of efficacy, AE, study drug dispensing, etc.), appropriate assessments may be performed based on the medical judgment of the investigator. Assessments that are included in the protocol schedule of assessments will be recorded in the CRF. After an unscheduled visit, the regular scheduled study visits must continue according to the planned visit and assessment schedule.

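### SAP Table 4 counts 30-day months from Month 12 while protocol visits fall every 182 days, so unscheduled visits can increasingly replace scheduled ones in by-visit summaries

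*SAP*

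**What the plan says.** **Protocol.** The footnotes to the visit schedules (Tables 1 and 2) state that "6 months correspond to 26 weeks". Section 3.10.3.1 adds "From Visit 5 onwards, all following visits are scheduled every 6 months", with a tolerance of 7 days either way. Section 3.10.6 allows extra visits at any time: "Depending on the reason for the unscheduled visit (e.g., loss of efficacy, AE, study drug dispensing, etc.), appropriate assessments may be performed". Results of assessment types that belong to the schedule go into the CRF.

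**SAP.** Section 5.1.1 presents Table 4 as giving the windows and target days of the protocol's visits. The row for Visit 5 reads "Week 26 | 148 to 270 | 182", which is 26 weeks. The next row reads "Month 12 | 271 to 450 | 360", and every later target is 30 times the month number (Month 60: 1800). Where a window holds several visits, the rule is "If a participant has 2 or more actual visits in 1 visit window, the visit closest to the target day will be used". Of the rest it says "The other additional visit(s) will not be used in the summaries or analyses", although they may still serve to determine clinically important endpoints. Nothing separates scheduled from unscheduled visits. The outputs concerned are the by-visit laboratory values and changes from baseline (5.5.3.1) and the by-visit vital signs (5.5.3.2).

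**The concern.** Two calendars are in use. Visits happen every 182 days, and the analysis looks for them every 180. The gap is trivial at first but accumulates, and long-term follow-up is the purpose of this study. With a nearest-visit rule, a growing gap leaves an on-time scheduled visit ever easier to beat.

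Unscheduled visits are not a random sample of occasions. Some are prompted by an adverse event or loss of efficacy; others are for drug dispensing or up-titration. If they replace scheduled visits more often as time passes, the late columns of the by-visit tables mix routine and prompted measurements in a proportion that changes with time. A single-arm study has no concurrent control against which such a change would show.

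**Working it through.** **Inputs**
- Visit interval: 26 weeks = 182 days, tolerance ±7 days (protocol Tables 1 and 2, 3.10.3.1). I take visits as counted from Visit 1.
- SAP target 30n for Month n, window 30n − 89 to 30n + 90; ties go to the later visit (SAP 5.1.1).
- Rate of unscheduled visits: not in the documents. Assumed 0.25 to 2 per year.

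**1. Reproduce Table 4.** For n = 12 the rule gives target 360 and window 271 to 450; for n = 60, 1800 and 1711 to 1890. All nine rows from Month 12 to Month 60 reproduce. Week 26 is the exception: the 30-day rule would give 180, and the table has 182.

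**2. Drift.** The k-th half-yearly visit (n = 6k) falls at 182k against a target of 180k, so the drift is 2k days from k = 2: 4 at Month 12, 12 at Month 36, 20 at Month 60 (1820 against 1800), 36 at Month 108 and 40 at Month 120. The study-day definition in SAP 5.1.2 adds 1, so the offset can be one day larger.

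**3. Windows still hold.** An on-time visit leaves its window only when 2k > 90, that is, at the 46th half-yearly visit.

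**4. Chance of replacement, given one unscheduled visit.** Let the scheduled visit lie D = 2k + U(−7, 7) days from target, and the unscheduled visit be uniform over the 179-day span of the window. The unscheduled visit is nearer with probability 2·E|D|/179.
- Month 12: E|D| = (11² + 3²)/28 = 4.64, giving 5.2%.
- Month 36: 2 × 12/179 = 13.4%.
- Month 60: 2 × 20/179 = 22.3%.
- Month 120: 2 × 40/179 = 44.7%.
- Targets at 182k: E|D| = 3.5, giving 3.9% at every visit.

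**5. Cross-check in whole days.** A scheduled visit d days after target loses to any visit on 2d − 1 days: 7 at Month 12, 39 at Month 60 (21.7% of 180) and 71 at Month 108 (39.4%).

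**6. Chance of replacement per window.** With r unscheduled visits per year, P = 1 − exp(−r × days/365.25). Averaged over the ±7-day tolerance, the displacing days are 8.9 at Month 12, 39 at Month 60, 71 at Month 108 and 7.0 with aligned targets. Example, Month 60 with r = 2: 1 − exp(−2 × 39/365.25) = 19.2%.

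| r per year (assumed) | Month 12 | Month 60 | Month 108 | Aligned targets, any visit |
|---|---|---|---|---|
| 0.25 | 0.6% | 2.6% | 4.7% | 0.5% |
| 0.5 | 1.2% | 5.2% | 9.3% | 1.0% |
| 1 | 2.4% | 10.1% | 17.7% | 1.9% |
| 2 | 4.7% | 19.2% | 32.2% | 3.8% |

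**7. Are late visits reachable?** Enrolment ran from 07 July 2010 to 02 September 2014 (SAP 1.2). By the 01 September 2019 cut-off (SAP 1), the first entrant could have 3343 days (past the Month 108 visit at 3276) and the last 1825 (past the Month 60 visit at 1820).

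**The case against.** The strongest reply is that the arithmetic is right but little follows from it.

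- **No rate is given.** Replacement needs an unscheduled visit close to the target. The documents support *can replace*, not *does replace*. This stands. At every rate tried, the scheduled visit is still the one used in most windows.
- **Not all replacement is due to drift.** Suppose 20% of participants have one unscheduled visit in a window (assumption). Replacement at Month 60 is then 20% × 22.3% = 4.5%, of which 20% × 3.9% = 0.8% would occur anyway, leaving about 3.7% for drift. This stands.
- **A late drug effect.** A reader might infer that the tables would show a false one. The documents do not support that. If replaced haemoglobin values differed by 5 to 20 g/L (assumption), 3.7% drift-related replacement would move the Month 60 mean by only about 0.2 to 0.7 g/L. The study is descriptive: "No formal hypothesis testing will be conducted".
- **Blanked laboratory values.** A reader might infer that an unscheduled visit without a blood sample deletes the scheduled result. The rule is worded by visit, but Table 4 is set out for safety parameters and the SAP does not say this happens. It is an ambiguity.
- **The main endpoints are untouched.** Adverse-event and survival analyses do not use visit windows, and worst-value laboratory abnormalities include unscheduled results. Markedly abnormal vital signs are also reported over the whole treatment period. This stands.
- **The late months are thin.** Month 120 needs 3640 days, beyond the 3343 available to the first entrant at the 2019 cut-off, and treatment ends on local commercial availability. No numbers at risk are given. The 45% figure marks where the rule leads, not a typical visit.
- **Participants who started selexipag in A302.** In the Selexipag-treated set their Day 1 lies in A302, whose schedule is not in these documents. They are 574 of 953, of whom 330 entered A303. Their offset cannot be derived, and new targets need not align them.

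These points limit size and scope. They do not remove the mismatch or supply a rule that protects scheduled values.

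**Conclusion.** The point holds in limited form. From Month 12 the target days in Table 4 are not those of the protocol, and the gap grows by 2 days per half-year. This applies to the 709 participants of the open-label set and the 379 ex-placebo participants of the Selexipag-treated set. For any constant non-zero rate of unscheduled visits, the chance that one replaces an on-time scheduled visit rises with follow-up, whereas aligned targets would keep it flat. The actual size depends on a rate the documents do not give.

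The consequence is confined to by-visit laboratory and vital-sign summaries. On-time visits are not mislabelled. The conditional percentages also assume that unscheduled visits are spread evenly over the window. The correction is still worthwhile, because these tables describe long-term safety and the distortion increases with time.

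**What to change.** In SAP 5.1.1:

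1. From Month 12, set the Table 4 targets to 182 × (n/6) days (364, 546, 728, ... 1820) with boundaries at the midpoints. The window for the k-th half-year becomes 182k − 90 to 182k + 91, for example 274 to 455 at Month 12 and 1730 to 1911 at Month 60. The Week 26 window then ends at day 273 instead of 270.
2. Select by parameter. Within a window take the non-missing value from a scheduled visit, the nearest to target if there are several. Use an unscheduled value only if there is no scheduled one.
3. State that unscheduled values still count in the worst-value and treatment-emergent abnormality tables.

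The second change by itself prevents replacement and also covers participants who started selexipag in A302. The cost is one table, one selection rule and reprogramming of visit assignment. No new data are needed. By-visit figures may differ slightly from earlier submission tables, which a footnote can explain.

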5.1.2. Study Day and Relative Day

Study day or relative day for a visit is defined as:

- Visit date - date of Study Day 1 + 1, if visit date is \geq date of Study Day 1
- Visit date - date of Study Day 1, if visit date $<$ date of Study Day 1

There is no 'Day 0'.

The Study Day 1 for OLS and STS periods is defined in Sections [5.1.3.1](#) and [5.1.3.2](#).

5.1.3. Study Day 1 and End of Treatment

5.1.3.1. For Treated Set - OL

Study Day 1 (or Day 1) refers to the start date of the first study intervention administration in A303, as defined in Section 4. If the start date is missing, the date of Visit 1 in CRF will be used.

End of treatment (EOT) refers to the date of the last selexipag administration in A303.

5.1.3.2. For Selexipag treated Set

Study Day 1 (or Day 1) refers to the start date of the first selexipag administration in either A302 or A303 (whichever is earlier), as defined in Section 4. If the start date is missing, the date of Visit 1 of A302 or A303 (whichever is earlier) in CRF will be used.

EOT refers to the date of the last selexipag administration in A302 or A303, whichever is later.

5.1.4. Last Contact Day

5.1.4.1. For A302 Participants not Entered in A303

The last contact date is defined as the latest of the following dates: Adverse Event start date; Hospitalization admission date; Death date; Any event date confirmed by the CEC; Clinical Worsening Event date; Study Intervention start / end dates; Disposition dates (from the CRF pages: “Survival Follow-up at Study Closure”, “Post-Treatment Observation Closure Visit”); and any visit-based assessments such as, but not limited to: ECG, laboratory, vital signs, 6MWT or questionnaires (Camphor, WHO FC, Borg Dyspnea score, etc.).

5.1.4.2. For A302 Participants Entered in A303

The last contact date is taken directly from A303 CRF page ‘Study completion’. If missing, the last contact date is defined as the latest of the following dates: Adverse Event start date; Death date; Study Intervention start / end dates; Visit dates (from the CRF page “Visit Log”); Disposition dates (from the CRF page “End of Study Visit”); and any visit-based assessments such as, but not limited to laboratory or vital signs.

5.1.5. Baseline definition

5.1.5.1. For Treated Set - OL

Baseline is defined as the last observation prior to or on the respective Study Day 1 (Section 5.1.3.1) of selexipag treatment start in A303.

5.1.5.2. For Selexipag treated set

Baseline is defined as the last observation prior to or on the respective Study Day 1 (Section 5.1.3.2) of selexipag treatment start in A302 or A303.

5.1.6. Imputation Rules for Missing AE Date/Time of Onset/Resolution

Partial AE onset dates in A302 and A303 will be imputed as follows:

- If the onset date of an AE is missing day only, it will be set to:
 - First day of the month that the AE occurred, if month/year of the AE onset is different from the month/year of the study intervention start
 - The day of study intervention start (A302/A303), if the month/year of the AE onset is the same as month/year of the study intervention start date and month/year of the AE resolution date is different
 - The day of study intervention start or day of AE resolution date, whichever is earliest, if month/year of the AE onset and month/year of the study intervention start date and month/year of the AE resolution date are the same
- If the onset date of an AE is missing both day and month, it will be set to the earliest of:
 - January 1 of the year of AE onset, as long as this date is on or after the study intervention start date
 - Month and day of the study intervention start date, if this date is in the same year as the AE onset
 - Last day of the year if the year of the AE onset is prior to the year of the study intervention start date
 - The AE resolution date.
- Completely missing onset dates will not be imputed.

If the AE resolution dates is partial it will be imputed as follows:

- If the resolution date of an AE is missing day only, it will be set to the earliest of the last day of the month of resolution or the day of the death date, if the death occurred in that month.
- If the resolution date of an AE is missing both day and month, it will be set to the earliest of December 31 of the year or the day and month of the death date, if the death occurred in that year.
- Completely missing resolution dates will not be imputed.

The approach described above (the Janssen standard approach) will give reasonable imputed values for partial missing onset dates.

5.2. Participant Dispositions

The following disposition categories (derivable from 'Study Completion' page of CRF) will be summarized (taking the information from the last available A302/A303 study) for both OLS and STS (A302+A303):

- Participants who completed the study (attended EOS visit)
- Participants who terminated study participation prematurely
- Reason for termination of study participation*[^]
- Participants who completed study intervention

- Participants who discontinued study intervention
- Reasons for discontinuation of study intervention*[^]

NOTE: *The A302 protocol has “end of study” (EOS) visit before the “end of treatment in TEP (Treatment Extension Period)” visit. The reason(s) for discontinuation of study intervention / termination of study will be taken from the last available information (at EOS or end of TEP visit) in A302.

[^]Unknown reason for discontinuation will be summarized by “Chinese participants” and “Other participants”.

A listing of participants who terminated study participation prematurely will be generated, separately, for OLS and STS (A302+A303).

A listing of participants who discontinued study treatment prematurely will be generated, separately, for OLS and STS (A302+A303).

5.3. Primary Endpoint(s) Analysis

No primary efficacy endpoint.

5.4. Secondary Endpoint(s) Analysis

No secondary efficacy endpoints.

5.5. Safety Analyses

All safety analyses will be summarized using OLS and STS (A302+A303) based on actual treatment received, unless otherwise specified. All results of OLS and STS (A302+A303) will be summarized in the same tables as displayed in Section 4, unless otherwise specified.

For all continuous safety variables, descriptive statistics will include the N, mean, standard deviation, median, minimum, and maximum. Categorical variables will be summarized using frequency counts and percentages.

Additional analyses are specified in Section 5.5.3.

5.5.1. Extent of Exposure

Study intervention duration in days is defined as [End date of study intervention] – [Start date of study intervention] + 1 (Section 5.1.3), and in months as (duration in days / 30.4). Subject-years of treatment are calculated as (duration in days/ 365.25). The total subject-years of a treatment group is the sum over individual participants of that treatment group.

The number and percentage of participants who receive the study intervention will be summarized. Study intervention duration and subject-years of treatment will be summarized with N, mean, SD, median, and range (minimum, maximum).

In addition, frequency for participants with cumulative study intervention duration ≥ 1 month, ≥ 3 months, ≥ 6 months, ≥ 12 months (every 12 months after this) will also be summarized.

Descriptive statistics of study intervention duration will be presented overall as well as by categories of Individual Maximum Tolerated Dose (IMTD), as defined in Section 5.5.1.1. In addition, descriptive statistics for IMTD will be presented, overall and by categories of IMTD (Section 5.5.1.1).

5.5.1.1. Definition of IMTD

The IMTD (mcg b.i.d.) is defined by the following rules regardless of length of the titration period:

- Participants who entered the study defined maintenance period (=who completed the study titration period, Section 6.10):
 - IMTD is defined as the last b.i.d. dose at the end of titration period
- Participants who did not enter the study defined maintenance period (=who withdrew from the study during the study titration period, Section 6.10):
 - IMTD is defined as the highest b.i.d. dose without dose reduction afterward.
 - If no up-titration attempted, IMTD is defined as zero.

The IMTD (mcg b.i.d.) categories are defined for both STS (A302+A303) and OLS as

- 0
- 200-400
- 600-1000
- 1200-1600

